OFFICIAL TITLE OF STUDY: Targeting Attention Orienting to Social Threat to Reduce Social Anxiety in Youth

NCT NUMBER: 03932032

DATE: 03-10-2026

[figure not shown]
PROTOCOL

The primary goal of this 2-site (Florida International U; Yale U) R01 project is to confirm attention bias modification treatment (ABMT) as an efficacious treatment for social anxiety disorder (SAD) in children and adolescents (i.e., “youth”) ages 10 to 14 years. We will randomize N=260 youths (130 each site) to 8 sessions of either ABMT or Neutral Control Task (NCT) delivered twice weekly for 4 weeks, with 160 trials per session. At pre-treatment (PRE), post-treatment (POST), and 6-month Follow-Up, we will assess the target, specifically, P1 amplitudes for socially threatening stimuli, and social anxiety symptom severity rated by independent evaluators (IEs), youths, and parents.

- Aim 1: Demonstrate target engagement. Hypothesis 1:** P1 amplitudes for socially threatening stimuli in the dot-probe task will be significantly lower at POST in the ABMT arm compared with the NCT arm.
- Aim 2: Demonstrate effects of ABMT on social anxiety symptom severity. Hypothesis 2a.** Social anxiety symptom severity rated by IEs, youths, and parents at POST will be significantly lower in the ABMT arm compared with the NCT arm. **Hypothesis 2b.** Youth ratings of state anxiety measured during a social evaluative stress task at POST will be significantly lower in the ABMT arm compared with the NCT arm.
- Aim 3: Demonstrate target validation. Hypothesis 3:** P1 amplitudes for socially threatening stimuli in the dot-probe task will mediate reductions in social anxiety symptom severity.
- Aim 4: Evaluate maintenance of target engagement, effects on social anxiety symptom severity, and target validation. Hypothesis 4:** Target engagement, effects on social anxiety symptom severity, and target validation will be maintained at 6-month Follow-Up evaluation.

APPROACH

See Figure 1 for the randomized controlled design and Table 1 for the measures administered at each assessment. Following parental consent and child assent, youths and parents will be administered interviews and questionnaires (see Measures) and youths will complete the dot-probe task while EEG/ERP data are collected (PRE). Youths will also be administered a measure of state anxiety immediately before a social stress task at PRE.

Subjects will be randomized 1:1 to two study arms: ABMT or NCT. Subjects in each arm will complete 8 sessions over 4 weeks. Number and duration of sessions will be identical in both arms. We will collect data on the target variable (P1 amplitudes) and the outcomes (social anxiety symptom severity) from the youths and parents one week after treatment ends (POST). At POST, youths will also be re-administered a measure of state anxiety immediately before a social stress task. Six months after the POST assessment, youths and parents will once again be administered all measures including the dot-probe task while EEG/ERP data are collected and a social stress task (Follow-Up).

Subjects

Two-hundred sixty youths ages 10 to 14 years with SAD will be admitted to the study (n=130 at each site). **Inclusion Criteria.** (A) Be between ages 10 and 14 years; (B) meet DSM5 criteria for a diagnosis of SAD; (C) cease other psychosocial treatment; (D) presence of any coexisting psychiatric diagnoses must be of lesser severity than SAD; and (E) have no current psychotropic medication other than a stable dose of stimulant or non-stimulant medication for coexisting ADHD.

Exclusion Criteria. (A) meet for Autism Spectrum Disorder, Intellectual Disability, Bipolar Disorder, Tourette’s Disorder, Psychotic Disorders, or Substance Use Disorders; (B) show high likelihood of hurting themselves or others; (C) be a victim of undisclosed abuse requiring investigation/supervision by Social Services; (D) have a history of neurological illness, including seizures/epilepsy, or head injury with loss of consciousness ≥ 5 minutes; or (E) have an uncorrected vision or physical disability that interferes with their ability to see stimuli presented briefly on a computer screen or click a mouse button rapidly.

Interventions

ABMT. Subjects assigned to the ABMT arm will complete 2 ABMT sessions a week for 4 weeks, for a total of 8 sessions. At each session, subjects complete 160 ABMT trials. In each ABMT trial (see Figure 5 for an example trial of ABMT), following a fixation cross, 2 faces of the same actor (one angry, one neutral), one above the other, are presented for 500ms. Next, a probe (< or >) appears in the location of the neutral face. Subjects press the left or right mouse button to indicate the orientation of the probe (< or >). The probe remains on the screen until subjects respond. Neutral face location, actor, and probe type will be fully counterbalanced.

NCT. Subjects assigned to the NCT arm will complete 2 NCT sessions a week for 4 weeks, for a total of 8 sessions. At each session, subjects will complete 160 NCT trials. In each NCT trial, following a fixation cross, 2 faces of the same actor (both neutral), one above the other, are presented for 500ms. Subjects press the left mouse button to proceed to the next trial.

Measures

I. Measure of Target: P1 amplitude elicited in the dot-probe task

Subjects will complete the dot-probe task. In the task, a pair of facial expressions (threatening-neutral or neutral-neutral) from the same actor is presented vertically for 500ms and then followed by a visual probe for 1000ms. The probe appears in the location of the previously viewed threatening face (i.e., congruent trials) or neutral face (i.e., incongruent trials for threatening-neutral trials). Subjects press the left mouse or right mouse button to indicate the orientation of the probe (< or >). Subjects complete 240 trials: 80 congruent, 80 incongruent, and 80 neutral. As in past studies, a different set of faces will be used in the dot-probe assessment task (i.e., not the same faces as in the training protocol). EEG/ERG data will be collected during completion of the dot-probe task.

a. Electrophysiological Recording. Subjects will be fitted with a 128-channel Geodesic Sensor Net (Electrical Geodesics Inc., Eugene, OR). Raw signal EEG will be collected continuously using NetStation 5.3. The raw signal will be amplified and sampled at 1 KHz with a band-pass filter of 0.1-100 Hz. Once impedance values are below 50 k Ω , EEG will be recorded continuously and referenced to Cz. After collection, data will be stored until offline processing. After acquisition, data will be re-referenced offline using an average reference.

b. Event-Related Potentials. EEG data will be analyzed offline using NetStation ERP Analysis Tools (5.3). In post-processing, EEG data will be re-filtered with a lowpass filter of 30 Hz. Ocular and motor artifacts exceeding ± 75 μ V will be rejected. Data will be segmented and visually inspected for additional ocular and motion artifact. Epochs containing blink activity will be removed as EOG contamination. Bad channels will be identified and interpolated. The entire trial will be excluded if more than 15 sensors are rejected or if other significant movement artifact occurs. Data will be re-referenced to average reference and baseline-corrected. Trials will consist of a 100 ms baseline period and 500 ms period following onset of facial stimuli. Exhaustive windows will be shaped by minima and maxima of peak onset ranges recorded per subject, and group-wise grand averages will be inspected to confirm the latency windows included all subjects' P1 component. Mean amplitude within the determined time window will be computed for Neutral-Threat stimuli.

II. Anxiety Outcome Measures

a. Independent Evaluator Ratings: Liebowitz Social Anxiety Scale for Children and Adolescents (LSAS-CA). The LSAS-CA is a widely used, psychometrically sound clinician-administered measure of social anxiety in youth.

b. Youth Self-Ratings and Parent Ratings: Screen for Child Anxiety Related Emotional Disorders (SCARED-C/P). The SCARED is a widely used, psychometrically sound measure of youth anxiety.

c. Youth State Anxiety Self-Rating before Trier Social Stress Task (TSST). We will use the State-Trait Anxiety Inventory for Children – State Subscale (STAIC-S) administered before the TSST to assess subjects' levels of state anxiety. The TSST is a widely used social stress task wherein subjects are told that they will give a video-recorded speech about their strengths and weaknesses and then are given three minutes to prepare for the speech. At the end of the three-minute preparation period, subjects will be administered the STAIC-S and will then complete the speech task.

STATISTICAL ANALYSIS PLAN

We will conduct a full missing values analysis (MVA) in order to identify variables that are related to missingness; these variables will be included as auxiliary variables in any analysis models to reduce bias due to missingness. The proposed analysis methods (i.e., multilevel regression with maximum likelihood estimation) are robust to MAR (missing at random) or MCAR (missing completely at random) mechanisms, which will minimize impact of missingness and attrition. If there is evidence of MNAR (missing not at random) patterns, we will use appropriate methods. We will assess whether data meet all assumptions of analysis (multivariate normality, outliers) prior to analyses. We will adjust for any violations using robust methods (such

as using bootstrap standard errors). We will evaluate group differences in potential covariates (e.g., sex, pubertal status, race/ethnicity, P1 amplitudes, social anxiety severity, comorbid diagnoses, treatment utilization) prior to analyses to assess randomization and will include these variables in models as needed. Analyses will use the combined dataset from the two sites. Site will be included as a covariate to adjust for any clustering effects. In general, mixed models (also called multi-level or growth models) will be used to assess change in outcome variables over time within each treatment arm. Preliminary models will include time, group, and the time x group interaction, which indicates whether the groups differ in their change over time (on average). We will evaluate models with random intercepts (allowing individuals to vary in their mean levels of the outcome) and random slopes (allowing individuals to vary in their change over time) and choose the best model using likelihood ratio (LR) tests. We will also evaluate models with non-linear change with respect to time (e.g., $\ln[\text{time}]$) and choose the best model using LR tests. We will use a Holm adjusted modified Bonferroni method for controlling experimentwise error rates; it is more powerful than traditional Bonferroni or Scheffe methods.¹⁷¹

Aim 1: Demonstrate target engagement. The effect of treatment group on P1 amplitudes will be assessed using a mixed model with P1 amplitudes as the (repeated) outcome =; group, time, and the group x time interaction will be included as predictors. The “time” variable will be centered at POST assessment, allowing us to evaluate group differences at that wave. The group effect represents the difference between groups at the POST assessment; significantly lower scores in the ABMT arm compared with the NCT arm would confirm target engagement.

Aim 2: Demonstrate effects of ABMT on social anxiety symptom severity. The same general procedures described in Aim 1 will be applied to Aim 2 data analysis. The effect of treatment group on social anxiety symptom severity will be assessed using a mixed model with social anxiety symptom severity as the repeated measure; group, time, and the group x time interaction will be included as predictors. The “time” variable will be centered at POST assessment, allowing us to evaluate group differences at that wave. Of interest is whether the contrast between study arms is statistically significant. The group effect represents the difference between groups at the POST assessment; significantly lower scores in the ABMT arm compared with the NCT arm would demonstrate the efficacy of ABMT. We will use the same analytic approach when examining subjects’ levels of state anxiety (STAI-C-S) before the TSST.

Aim 3: Demonstrate target validation. We will examine changes in P1 amplitudes as a mediator of the social anxiety reduction effect of ABMT using an extension of the approach described in Aims 1 and 2, within a larger structural equation modeling (SEM) framework. Within a single model, change in P1 amplitudes will be modeled as in Aim 1 and change in social anxiety symptom severity will be modeled as in Aim 2. In addition, the effect of the P1 amplitudes slope on both (a) the group effect on social anxiety symptom severity and (b) the group x time interaction on social anxiety symptom severity will be included. These additional effects (“paths”) will allow us to evaluate how change in P1 amplitudes relates to group differences in change in social anxiety symptom severity across the assessment waves, including at POST. Statistical significance of the mediated effect will be assessed using Monte Carlo methods.

Aim 4: Evaluate maintenance of target engagement, effects on social anxiety symptom severity, and target validation. This aim represents a test of the maintenance of ABMT effects over 6 months. The analysis is a variant on the approach used in Aims 1 and 2. The effect of treatment group on each outcome at 6-month Follow-Up will be assessed using a mixed model with the outcome as the repeated measures at 4 waves (3 waves for state social anxiety before performance on the TSST); group, time, and the group x time interaction will be included as predictors. The “time” variable will be centered at the final wave (Follow-up), so group effects will reflect group differences at the 6-month Follow-Up. Maintenance of effects will be demonstrated by significantly lower scores in the ABMT arm compared with the NCT arm. Using a variant on the approach used in Aim 3, we also will examine how change in P1 amplitudes relates to group differences in social anxiety symptom severity at Follow-Up.

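### Aim 3 prespecifies no adjustment for shared causes of P1 change and symptom change: the only criterion stated for candidate covariates is arm difference, which cannot identify them

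*Combined protocol and SAP*

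**What the plan says.** Hypothesis 3 is a causal statement: "P1 amplitudes for socially threatening stimuli in the dot-probe task will mediate reductions in social anxiety symptom severity". Under Aim 3, the SAP joins the Aim 1 and Aim 2 models (group, time, group by time) in one structural equation model and adds paths from the P1 slope to the symptom effects. The decision rule is: "Statistical significance of the mediated effect will be assessed using Monte Carlo methods". Aim 4 uses a variant of this at Follow-Up.

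The general text of the SAP, before Aim 1, governs covariates in three ways:

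- **Candidate covariates.** "We will evaluate group differences in potential covariates (e.g., sex, pubertal status, race/ethnicity, P1 amplitudes, social anxiety severity, comorbid diagnoses, treatment utilization" are compared between arms "to assess randomization and will include these variables in models as needed". No test, threshold or other criterion is given.
- **Site.** "Site will be included as a covariate to adjust for any clustering effects". This is unconditional.
- **Predictors of missingness.** "these variables will be included as auxiliary variables in any analysis models to reduce bias due to missingness".

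The documents name no variable as a confounder of P1 change and symptom change. They state no no-confounding assumption and plan no sensitivity analysis for it.

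**The concern.** Randomisation protects the effect of arm on P1 and the effect of arm on severity. It does not protect the path from P1 change to severity, because nobody is randomised to a P1 change. A variable that influences both (pubertal status or a comorbid diagnosis, for instance) biases that path even when it is perfectly balanced between arms.

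Under valid randomisation, whether the arms differ on a variable is a matter of chance. It carries no information about whether that variable is a shared cause. The screen therefore answers a different question from the one Aim 3 needs answered. Site and the missingness predictors are brought in for other reasons, and an auxiliary variable may not adjust the path at all.

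At stake is the target-validation claim. A significant product of the two paths could be reported as showing that P1 carries the treatment effect when the two changes merely share a cause. Aims 1 and 2 are not touched by this.

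**Working it through.** **Inputs from the documents.** N = 260, and "Subjects will be randomized 1:1 to two study arms: ABMT or NCT", so about 130 per arm. The documents give no alpha, sidedness, power, effect size, SD or dropout, so 260 cannot be re-derived. For orientation only: at 130 per arm and two-sided 0.05, the difference detectable with 80% power is (1.960 + 0.842) × √(2/130) = 0.347 SD.

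**Assumed inputs, shown as ranges.** ABMT lowers P1 change by d SD. P1 has no effect on severity. One measured baseline variable C correlates r with P1 change and r with severity change within arm. C enters only if the arm comparison gives p < 0.05. The mediated effect is tested with a 95% Monte Carlo interval. This is a single-change-score version of the planned model.

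**Step 1: the bias.** Without C, the within-arm regression of severity on P1 has expected slope r × r = r². The apparent mediated effect is then −d × r². With d = 0.35 and r = 0.4 it is −0.35 × 0.16 = −0.056. The simulation gives −0.056 without C and 0 with C. The negative sign reads as symptom reduction.

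**Step 2: a hand check at d = 0.35, r = 0.4.** Both paths must be significant.

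- Arm to P1: z = 0.35 / √(2/130) = 0.35 / 0.124 = 2.82, so the chance of exceeding 1.96 is about 0.81.
- P1 to severity: standard error = √((1 − 0.16²)/257) = 0.0616, z = 0.16 / 0.0616 = 2.60, so the chance is about 0.74.
- Product: 0.81 × 0.74 = 0.60. The simulated rate with no adjustment is 57%.

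**Step 3: the screen.** Simulated with 2,500 trials per setting, C passes the arm-difference screen in 4.2% to 5.8% of trials, whatever its strength as a confounder. That is just the level of the balance test.

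**Step 4: false mediation at N = 260, screen / always adjusted.**

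| P1 lowered by | r = 0 | r = 0.3 | r = 0.4 | r = 0.5 |
|---|---|---|---|---|
| 0 SD | 0.2% / 0.2% | 0.9% / 0.3% | 2.8% / 0.2% | 4.5% / 0.0% |
| 0.2 SD | 1.1% / 1.2% | 8.2% / 1.2% | 21.5% / 2.0% | 32.2% / 2.3% |
| 0.35 SD | 4.1% / 4.0% | 20.1% / 4.2% | 55.1% / 4.3% | 74.2% / 4.7% |
| 0.5 SD | 5.0% / 5.0% | 27.0% / 4.8% | 67.6% / 5.6% | 91.6% / 5.5% |

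Repeat runs at 0.35 to 0.4 SD give about 6–9% at r = 0.2, 22–24% at r = 0.3 and 56–62% at r = 0.4 under the screen, against about 3–6% with C always in. Simulation error is about ±2 points: at 55% and 2,500 runs, 1.96 × √(0.55 × 0.45 / 2500) = 0.02. Taken with the table, the ranges are 6–9%, 20–24% and 55–62%.

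**Step 5: variations at d = 0.35, r = 0.4.** A looser screen (p < 0.20) still gives 46%. With 208 analysed (20% loss assumed) the rate is 40%.

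**The case against.** **The plan does not say that balanced covariates are excluded.** A reader might infer a rule under which variables enter only if the arms differ. The text does not go that far: *as needed* is undefined and does not bar a balanced covariate. This stands. The supportable statement is that arm difference is the only criterion named and that no confounder of this path is prespecified. The vagueness is no safeguard, since it leaves the choice until the data are seen.

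**Baseline P1 and baseline severity are already in the joint model.** They are the first wave of each repeated outcome, and random intercepts are considered. This largely stands: they are not simply absent. What is unstated is whether the slope paths condition on those intercepts.

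**Much larger error rates are tempting.** Setting the residual correlation directly to 0.2 or 0.3, with P1 lowered by 0.4 SD, gives about 80% and 90% false mediation. One covariate produces a residual correlation of r², so these need r = √0.2 = 0.45 and √0.3 = 0.55, that is, 20% to 30% of the variance in both changes. Several covariates could add up, but the documents support no value, so those rates should not lead.

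**Conditions apply.** If ABMT does not move P1, the rate stays at or below 5%. Confounding in the opposite direction would not look like mediated benefit. Holm adjustment lowers the rates: at an assumed 0.05/3 and 0.4 SD, from 32% to 17% at residual correlation 0.1 and from 79% to 66% at 0.2. It does not remove the bias. All of this stands as limits on size. However, P1 being lowered is Hypothesis 1, the case in which Aim 3 matters most.

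**Conclusion.** The point holds in a limited form. Arm difference, the only stated criterion for candidate covariates, cannot identify confounders of the P1-to-symptom path, and nothing else in Aim 3 or its Aim 4 variant does. If ABMT lowers P1 and a shared cause mimics benefit, a significant mediated effect need not mean that P1 matters.

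The size is conditional. With P1 lowered by 0.35 to 0.4 SD, a weak shared cause (r = 0.2) raises the error only slightly, to 6–9%. A moderate one (r = 0.3 to 0.4) raises it to between 20% and 62%. These figures rest on assumed correlations and effect sizes, one measured confounder, a two-sided 0.05 test without Holm adjustment, and a simplified model. They show what the plan permits and do not predict what this trial will find. The SAP should be changed, because the remedy is cheap and target validation is one of the trial's four aims.

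**What to change.** For Aim 3 and its Aim 4 variant:

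1. Replace the arm-difference screen with a fixed set of baseline covariates already collected or known at PRE. An example is age, sex, pubertal status, comorbid diagnoses (including ADHD medication) and site. Enter the set in both the P1 and the severity equations, whatever the arm balance.
2. State how baseline P1 and baseline severity are handled. Either let the slope paths condition on both random intercepts, or use PRE as a covariate and not also as an outcome wave. Do not do both.
3. Report the residual P1–severity correlation at which the mediated effect would vanish, and word the target-validation conclusion in the light of it.
4. Do not add a free same-visit residual covariance between P1 and severity unless the repeated-wave model that identifies it is written out. In a single-change-score model it cannot be separated from the P1-to-severity path.

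The cost is SAP wording, a little more analysis and a few degrees of freedom. Adjustment deals with measured confounders only, which is why the sensitivity analysis in item 3 is needed.

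### The plan names no visit-specific covariance: if severity spread rises after PRE and then levels off or falls, and each visit mean is fitted, the model-based standard error at POST is about 5–15% too small

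*Combined protocol and SAP*

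**What the plan says.** The opening paragraph of the Statistical Analysis Plan sets the model family: "We will evaluate models with random intercepts (allowing individuals to vary in their mean levels of the outcome) and random slopes". The best model is picked by LR test, and non-linear time (for example ln time) is considered in the same way. The residual covariance is not described. Assumptions will be checked, with normality and outliers as the examples, and violations handled by robust methods such as bootstrap standard errors.

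Aims 1 and 2 centre time at POST and interpret the coefficient accordingly: "The group effect represents the difference between groups at the POST assessment". Aim 4 re-centres time so that "group effects will reflect group differences at the 6-month Follow-Up".

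Entry is by diagnosis: youths must "meet DSM5 criteria for a diagnosis of SAD", and any coexisting diagnosis must be less severe. No cut-off on an outcome score is given, and no SD at any visit.

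The number of waves is stated in two ways. The introduction has three: "At pre-treatment (PRE), post-treatment (POST), and 6-month Follow-Up, we will assess the target". Aim 4 has a "mixed model with the outcome as the repeated measures at 4 waves (3 waves for state social anxiety before performance on the TSST".

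**The concern.** A random intercept with one residual variance forces the same variance at every visit. A random slope with one residual variance gives the variance τ0² + 2τ01·t + τ1²·t² + σ², which is convex in its time variable. It can follow a steady rise, but not a sharp rise from PRE to POST followed by a plateau or fall.

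That second shape is plausible for symptom severity. Selection by diagnosis can compress severity at PRE, and nothing holds it compressed afterwards. The fitted POST variance is then pulled down towards the PRE variance.

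The Aim 1 and Aim 2 conclusions rest on the significance of the group effect at POST. If its standard error is too small, confidence intervals are too narrow and the test exceeds its nominal error rate before any Holm adjustment. The LR test offers no protection, because it compares only models that share the limitation.

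**Working it through.** **Inputs from the documents.** N = 260 and "Subjects will be randomized 1:1 to two study arms: ABMT or NCT", so 130 per arm. POST is one week after four weeks of treatment, and Follow-Up is six months after POST. I take these as weeks 0, 5 and 31.

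**Assumptions (not in the documents).** Complete data, two-sided 5% test, one residual variance, PRE SD = 1, later SDs as tabulated. Correlations are 0.6 (PRE–POST), 0.5 (PRE–Follow-Up) and 0.7 (POST–Follow-Up), with 0.4/0.3/0.6 as a second set. The plan gives no alpha, SD or standard error, so there is no figure to reproduce.

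**Step 1: which mean model gives the POST difference.** Suppose the arm difference is 0 at PRE and d at both POST and Follow-Up, which is a maintained effect as in Hypothesis 4. With complete data and one time term, the fitted difference is a least-squares line.
- Weeks: mean 12, deviations −12, −7, 19. Slope = 12d/554 = 0.0217d. Fit at POST = 0.667d − 7 × 0.0217d = 0.52d.
- ln(week + 1): values 0, 1.792, 3.466, deviations −1.753, 0.039, 1.713. Slope = 1.752d/6.008 = 0.292d. Fit at POST = 0.667d + 0.039 × 0.292d = 0.68d.

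Under a maintained effect, then, the coefficient is the POST difference only if all three visit means are fitted. The plan's non-linear option allows this but does not commit to it.

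**Step 2: standard error with each visit mean fitted.** The estimate is then the POST mean difference whatever covariance is used, so

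SE ratio = √(model POST variance / true POST variance), and actual error = 2 × (1 − Φ(1.96 × ratio)).

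The random-intercept model variance is the average of the three variances. For SDs 1/1.3/1.3 this is (1 + 1.69 + 1.69)/3 = 1.46, an SD of 1.208, so the ratio is 1.208/1.3 = 0.929. The standard error is 1.208 × √(2/130) = 0.150, against a correct 0.161. The random-slope variances come from the large-sample maximum likelihood fit, with the slope in weeks, wave number or ln time.

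| SDs PRE/POST/Follow-Up | Random intercept: ratio, error | Random slope: ratio, error |
|---|---|---|
| 1/1.2/1.2 | 0.948, 6.3% | 0.914–0.924, 7.0–7.3% |
| 1/1.3/1.3 | 0.929, 6.9% | 0.887–0.909, 7.5–8.2% |
| 1/1.5/1.5 | 0.903, 7.7% | 0.847–0.887, 8.2–9.7% |
| 1/1.4/1.2 | 0.865, 9.0% | 0.855–0.861, 9.1–9.4% |
| 1/1.25/1.5 | 1.013, 4.7% | weeks 0.910, 7.5%; wave or ln 0.968–0.973, 5.6–5.8% |
| 1/1.2/1.6 | 1.076, 3.5% | weeks 0.931, 6.8%; wave or ln 1.017–1.023, 4.5–4.6% |
| 1/1.1/1.5 | 1.108, 3.0% | weeks 0.967, 5.8%; wave or ln 1.046–1.052, 3.9–4.0% |

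The table uses the first correlation set. Over both sets, the highest errors in the first four rows are 7.4%, 8.2%, 9.7% and 9.5%. An unstructured covariance gives ratio 1.000 and 5.0% in every row.

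**Step 3: PRE and POST only.** With a random intercept and POST SD s, the ratio is √(((1 + s²)/2)/s²). For s = 1.2, 1.3 and 1.5 this is 0.920, 0.892 and 0.850, giving errors of 7.1%, 8.0% and 9.6%. A random slope has four variance parameters for three moments. Its components are not separately identified, but its fitted covariance is exact (ratio 1.000).

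**Step 4: one time term, three waves, SDs 1/1.2/1.2 to 1/1.5/1.5.** A random slope gives about 5.0% with linear or ln time. A random intercept with ln time gives 5.1–5.2%. A random intercept with linear time errs the other way at POST, at 3.5–4.3% over the settings examined.

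**Step 5: would the planned LR test notice?** In the plateau cases, a random slope on wave number or ln time still trails the unstructured model by an LR statistic of about 11 to 33 on 6 − 4 = 2 degrees of freedom (5% critical value 5.99). That comparison is not in the plan.

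**The case against.** A reader might infer that the standard error is too small whenever the coefficient really is the POST difference. The documents do not support that, for four reasons.

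- **Mean model.** The aims specify group, time and their interaction, and the only non-linear form named is ln time. With one such term and a random slope, the error is about 5%. If the visit means do follow that curve, the coefficient is also the POST difference and the test is valid.
- **Direction.** If spread keeps rising to Follow-Up, the random-intercept standard error at POST is correct or up to 11% too large. Random slopes on wave number or ln time stay within about 3–5% of the truth.
- **Premises.** No SDs are given, and one residual variance is inferred. Selection on diagnosis need not restrict P1 amplitude or STAIC-S, so the case is weaker for those outcomes. Nothing says that Follow-Up data are left out of Aims 1 and 2, so the PRE/POST-only case is a possible reading, not a stated plan.
- **Safeguard.** The plan promises robust methods, such as bootstrap standard errors, when assumptions fail. Resampling whole subjects would correct this standard error.

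These points stand and limit the claim, but they do not remove it. By Step 1, a maintained effect is the setting in which one time term misses the POST difference and a curve through all three means is needed. That is also the setting of the first four table rows. The safeguard applies only after a violation is detected, and variance over time is not among the named checks.

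**Conclusion.** The narrower point holds. Three conditions are needed: severity spread that rises from PRE to POST and then levels off or falls, a mean model that fits each visit, and no subject-level robust standard error. Every random-intercept or random-slope option examined then understates the POST standard error by about 5–15%, and a nominal 5% test runs at about 6–10%. A PRE/POST-only random-intercept analysis gives 7–10%.

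The size rests on assumed POST SDs of 1.2 to 1.5 times the PRE SD and on one residual variance. With equal SDs the random-intercept ratio is 1. The argument is strongest for LSAS-CA and SCARED.

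Aim 4 is exposed too. With SDs 1/1.25/1.5, a retained random intercept is about right at POST, but its Follow-Up ratio is 1.267/1.5 = 0.84. As written, the validity of the standard errors depends on an unstated residual structure, the time coding and a pre-test.

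**What to change.** First reconcile the three waves in the introduction with the four in Aim 4, because the size of the covariance matrix depends on it. Then, for the Aim 1, 2 and 4 contrasts, replace the LR choice between random intercepts and random slopes with a prespecified unstructured covariance across the assessment waves, common to both arms. State subject-level robust (sandwich) or bootstrap standard errors as the fallback if the model does not converge. Keep random slopes for the Aim 3 structural equation model, which needs a P1 slope.

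The cost is about one sentence in the SAP. With three waves there are six covariance parameters instead of four, which is minor with 260 youths. If spread does rise and then plateau, intervals at POST widen by about 5% (1/0.95) to 18% (1/0.85), which is their correct width. The change addresses the standard error only and does not settle the shape of the mean over time.
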